#### Cessation of CIC

CIC should only be discontinued when both of the following criteria are fulfilled:

- The subject does not have any associated symptoms which in the opinion of the investigators/subinvestigators require CIC; and
- The PVR is < 350 mL.

Upon discontinuing CIC, the subject will be seen at a follow-up visit 1 week later, when the results of PVR measurement, associated symptoms, and a urine analysis with a urine reagent strip are reassessed while urinalysis, urine culture and sensitivity test are performed for reassessment at the central laboratory. The investigators/subinvestigators will determine whether the subject can then be followed at regularly scheduled study visits or whether additional visits should occur based on PVR and/or associated symptoms.

#### **Definition of AE urinary retention**

An adverse event of urinary retention should only be recorded according to the following criteria when a subject has a raised PVR that requires protocol-specified intervention with CIC:

- Subject has a PVR of  $\geq 350$  mL (regardless of symptoms); or
- Subject has a PVR  $\geq 200$  mL and  $< 350$  mL and the subject reports associated symptoms (e.g., voiding difficulties and sensation of bladder fullness) that in the opinion of the investigators/subinvestigators require CIC.

#### **Definition of AE residual urine volume increased**

An adverse event of residual urine volume increased should be recorded if, in the opinion of the investigators/subinvestigators, the raised PVR is clinically significant but does not fulfill the above definition for urinary retention.

#### **7.4.8. Kidney and bladder ultrasound**

The kidney and bladder ultrasound study will be performed according to the study schedule. In order to assess the presence of stones in the kidneys and bladder, an ultrasound of these structures (with the bladder at least half full) will be performed.

Subjects will be excluded from this study if the screening ultrasound demonstrates the presence of bladder stones. In the case of unclear findings in an ultrasound study, other diagnostic measures (e.g., x-ray) may be required in order to confirm the presence of bladder stones. If a stone is detected in subjects after the injection of the investigational product, the event must be recorded as an adverse event in the CRF. Subjects developing stones while on study should be followed and treated according to the standard procedure at each study site.

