**CONCURRENT CONDITIONS/MEDICAL HISTORY (INCLUDES LIVER FUNCTION AND QTc INTERVAL)**

1. Patient has symptoms of OAB due to any known neurological reason (e.g., spinal cord injury, multiple sclerosis, cerebrovascular accident, Alzheimer's disease, Parkinson's disease, etc)
2. Patient has a predominance of stress incontinence determined by patient history.
3. Patient has a history or evidence of any diseases, functional abnormalities or bladder surgery, other than OAB, that may have affected bladder function including but not limited to:

1) Bladder stones (including bladder stone surgery) within 6 months prior to screening or confirmed occurrence of bladder stones at the screening phase

2) Surgery (including minimally invasive surgery) within 1 year of screening for stress incontinence or pelvic organ prolapse

3) Current use of an electrostimulation / neuromodulation device for treatment of urinary incontinence. Note: Use of any implantable device is prohibited within 4 weeks prior to initiation of screening phase and throughout the study period. Use of any external device is prohibited within 7days prior to the start of the screening phase

4) History of interstitial cystitis, in the opinion of the investigator (or subinvestigator)

5) Past or current evidence of hematuria due to urological / renal pathology or uninvestigated hematuria b

6) Past or current history of bladder cancer or other urothelial malignancy, positive result of urine cytology or uninvestigated suspicious urine cytology results c at the Screening phase.

7) An active genital infection, other than genital warts, either concurrently or within 4 weeks prior to Screening

8) Male with previous or current diagnosis of prostate cancer or a prostate specific antigen (PSA) level of >10 ng/mL at Screening d

9) Evidence of urethral and/or bladder outlet obstruction, in the opinion of the investigator (or subinvestigator)

4. Patient has a history of 2 or more urinary tract infections (UTIs) within 6 months of initiation of Treatment phase 1 (Week 0) or current administration of prophylactic antibiotics to prevent chronic UTIs

5. Patient has a positive urine dipstick reagent strip test at initiation of Treatment phase 1 (Week 0) for nitrites or leukocyte esterase, or who are considered by the investigator (or subinvestigator) to have UTI

6. Patient has a serum creatinine level >2 times the upper limit of normal (ULN) at screening

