### 12.3. Appendix 3: Definition of and Procedures for Recording, Evaluating, Follow-up and Reporting of Adverse Events

#### 12.3.1. Definition of Adverse Events

##### Adverse Event Definition:

- An AE is any untoward medical occurrence in a patient or clinical investigation subject, temporally associated with the use of a medicinal product, whether or not considered related to the medicinal product.
- NOTE: An AE can therefore be any unfavorable and unintended sign (including an abnormal laboratory finding), symptom, or disease (new or exacerbated) temporally associated with the use of a medicinal product.

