##### Events NOT meeting definition of an AE include:

- Any clinically significant abnormal laboratory findings or other abnormal safety assessments which are associated with the underlying disease, unless judged by the investigator to be more severe than expected for the subject's condition.
- The disease/disorder being studied or expected progression, signs, or symptoms of the disease/disorder being studied, unless more severe than expected for the subject's condition.
- Medical or surgical procedure (e.g., endoscopy, appendectomy): the condition that leads to the procedure is an AE.
- Situations where an untoward medical occurrence did not occur (social and/or convenience admission to a hospital).
- Anticipated day-to-day fluctuations of pre-existing disease(s) or condition(s) present or detected at the start of the study that do not worsen.

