8.5.5. Ultrasound

The listing of kidney and bladder ultrasound data will be prepared.

Listing will display the date of morphology, Yes / No for “Was the subject detected kidney stone?” and Yes / No for “Was the subject detected bladder stone?” at least.

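### Protocol 7.4.8 does not limit its stone adverse-event rule to new or worsened stones, so an unchanged kidney stone known from screening may be recorded as a post-treatment AE

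*Protocol*

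**What the plan says.** Protocol 7.4.8 gives the purpose of the scan as follows: "In order to assess the presence of stones in the kidneys and bladder". The exclusion is narrower than the imaging: "Subjects will be excluded from this study if the screening ultrasound demonstrates the presence of bladder stones". Exclusion criterion 3.1 in Section 5.2 agrees, naming only this: "Bladder stones (including bladder stone surgery) within 6 months prior to screening or confirmed occurrence of bladder stones at the screening phase". Kidney stones are not a named exclusion in either place.

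The recording rule in 7.4.8 is: "If a stone is detected in subjects after the injection of the investigational product, the event must be recorded as an adverse event". It does not say kidney or bladder, and it does not refer back to the screening scan. The next sentence deals with care: "Subjects developing stones while on study should be followed and treated according to the standard procedure at each study site".

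Appendix 3 (12.3.1) counts as an AE a "disease (new or exacerbated) temporally associated with the use of a medicinal product".

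SAP 8.5.5, in both the April 2018 version and the July 2018 amendment, provides this for the scans: "The listing of kidney and bladder ultrasound data will be prepared". That listing carries a Yes/No answer on whether a kidney stone was detected, and another for bladder stones. SAP 11.4.2 states that no treatment-emergent flag is defined. SAP 11.4.1.2 places AEs in treatment cycles by their start date.

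**The concern.** A rule worded as *must* leaves a site little room to ask whether the stone was already there. A subject can enter with a kidney stone on the screening scan, have the same stone seen at a later scan, and acquire an AE although nothing has changed. The general definition in Appendix 3 would not make that finding an AE.

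Kidney and bladder ultrasound is a named safety assessment in Section 3. Because the SAP only lists the scans, the AE tables are the only place where stones are tabulated. If those tables mix unchanged baseline stones with new ones, the reported incidence is hard to interpret, and it may vary with how each site read the sentence.

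**Working it through.** The plan states no figure on this point, so the check is a comparison of texts.

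**Step 1. The two recording rules, case by case.**

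- *Bladder stone at screening.* The subject is excluded, so no conflict arises.
- *No stone at screening, stone seen later.* It is an AE under 7.4.8. It is also an AE under Appendix 3, which counts a condition first found after treatment even if it may have been present before. The rules agree.
- *Kidney stone at screening, worse later.* It is an AE under 7.4.8, and an AE under Appendix 3 as an exacerbation. The rules agree.
- *Kidney stone at screening, unchanged later.* It is an AE under the literal wording of 7.4.8. It is neither new nor exacerbated, so it is not a disease AE under Appendix 3. The rules disagree.

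The conflict is confined to the last case.

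**Step 2. Can that case occur?** Yes. Only bladder stones are named as exclusionary. Some subjects with kidney stones may still be kept out by the open wording of criterion 3, by the haematuria item (3.5) or by investigator judgement (criterion 26), but none of these names kidney stones.

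**Step 3. Does *detected* settle it?** No. It can mean newly found. It can also mean seen at this scan, which is a natural reading of the Yes/No item in SAP 8.5.5. Other parts of Section 7.4 set study-specific AE rules: UTI is recorded whether or not there are symptoms (7.4.6.2.2), and urinary retention is defined by fixed PVR criteria (7.4.7). A site could reasonably take 7.4.8 as another such rule that overrides the general definition.

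**Step 4. Does the SAP catch it?** Only if the site dates the stone before the first injection, when 11.4.1.2 classes it as Pre-Treatment. If the site enters the date of the later scan, the event falls in treatment cycle 1 or a later cycle. No treatment-emergent flag corrects this. The display list (11.10) has no ultrasound table, and stones are not among the AEs of special interest (11.6.4).

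**Step 5. Size.** The documents give no prevalence, so any number is conditional. Let p be the share of the 240 randomized subjects with a kidney stone at screening, and suppose every such stone persists, is rescanned and is recorded as an AE:

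- expected spurious stone AEs = 240 × p
- p = 3%: 240 × 0.03 = 7.2
- p = 5%: 240 × 0.05 = 12
- p = 10%: 240 × 0.10 = 24

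The three values of p are assumptions, and the counts are upper-end figures for each. If every site applied Appendix 3, the count would be 0. For scale, the 5% cut-off for common AEs in SAP 8.1 is 0.05 × 240 = 12 subjects.

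**The case against.** The strongest reply is that 7.4.8 can be read consistently with Appendix 3. A stone documented at screening was detected before injection, so seeing it again is not a detection after injection. The next sentence speaks of stones that develop on study. The preceding sentences concern bladder stones, so the unqualified word may mean those alone, and known bladder stones are already excluded. Section 7.4.1 refers to Appendix 3 for the AE definition. Section 7.4.1.1 already allows findings that begin between consent and treatment to go to medical history. This stands as far as it goes: the sentence is ambiguous, and some sites will have read it this way. It does not show that all would.

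The documents do not support several stronger inferences that a reader might draw:

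- *That pre-existing stones are in fact counted as AEs.* The text allows this but does not establish it.
- *That Appendix 3's list of non-AEs flatly contradicts 7.4.8.* The phrase "condition(s) present or detected at the start of the study that do not worsen" belongs to an item about expected day-to-day fluctuations. It is not a general rule on unchanged conditions. The conflict rests on the words new or exacerbated.
- *That one stone is recorded afresh in each cycle.* Appendix 3 puts updates in the originally completed CRF, and SAP 11.4.1.2 assigns the cycle by start date.
- *That re-treatment is affected.* The criterion in Section 5.3 concerns bladder stones only, and the problem concerns kidney stones only.
- *That one arm is favoured.* With randomization and the same double-blind schedule, over-recording should be about equal in the two arms, leaving the absolute difference roughly unchanged.

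**Conclusion.** The point holds as an unresolved conflict between a specific recording rule and the general AE definition, limited to unchanged kidney stones seen at screening. The consequences are possible inconsistency between sites and possible inflation of kidney-stone AE incidence. Neither is shown to have happened.

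The size cannot be derived from the documents. It depends on the prevalence of kidney stones at screening, on how often they are seen again, on how sites read the sentence and on the onset date they enter. The counts above illustrate scale under assumed prevalences and are not estimates. No direction between arms is claimed. Efficacy, power, the significance level and the re-treatment criterion are untouched. It is a small safety-recording matter, worth correcting because the correction is cheap and the baseline scan needed for it is already collected.

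**What to change.** Reconcile 7.4.8 with Appendix 3. Reword the recording sentence so that a stone seen after injection is an AE when it was absent from the screening ultrasound or has worsened since then, and add a cross-reference to Appendix 3. State that stones seen at screening are recorded as medical history. A stone first found after treatment remains an AE, as Appendix 3 already provides.

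The cost is a sentence or two in the protocol, with no new visit, procedure or data item. If data are already in hand, kidney-stone AEs can be compared with the screening answer in the ultrasound listing. That identifies stones known at baseline, although a Yes/No item cannot show whether a stone has worsened.

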## 7.5. Other endpoints

### 7.5.1. Immunogenicity Testing

The investigators/subinvestigators will collect blood samples for neutralizing antibody testing according to the study schedule. Immunogenicity testing will be centrally performed at the central laboratory to which GSK outsources the analysis (Intertek Pharmaceutical Services and Pacific BioLabs). The samples will be stored at the central laboratory and sent to a laboratory in USA (Intertek Pharmaceutical Services) when samples in the screening period are collected from all subjects. At the laboratory, screening test will be performed to measure binding antibody (BaB). Positive BaB samples, determined based on the result of the measurement, will be sent to USA (Pacific BioLabs) separately, where a further test for definitive neutralizing antibody (NaB) positivity is performed. Similarly, when samples at the end of the study are collected from all subjects, immunogenicity testing will be performed according to the above-mentioned procedures.

## 8. DATA MANAGEMENT

- For this study subject data will be entered into GSK defined CRFs, transmitted electronically to GSK or designee and combined with data provided from other sources in a validated data system.
- Management of clinical data will be performed in accordance with applicable GSK standards and data cleaning procedures to ensure the integrity of the data, e.g., removing errors and inconsistencies in the data.
- Adverse events and concomitant medications terms will be coded using MedDRA (Medical Dictionary for Regulatory Activities) and an internal validated medication dictionary, GSKDrug.
- CRFs (including queries and audit trails) will be retained by GSK, and copies will be sent to the investigator to maintain as the investigator copy. Subject initials will not be collected or transmitted to GSK according to GSK policy.

## 9. STATISTICAL CONSIDERATIONS AND DATA ANALYSES

### 9.1. Hypotheses

The primary objective of this study is to evaluate the superiority of a single dose treatment of GSK1358820 100 U compared with placebo. The primary efficacy endpoint is the change from baseline in the daily average number of urinary incontinence episodes at week 12 after the first treatment. The major secondary efficacy endpoint is the change from baseline in the average volume voided per micturition at week 12 after the first treatment.

The primary null hypothesis is that there is no difference in the change from baseline of the daily average number of urinary incontinence episodes when treated with GSK1358820 compared to placebo. The primary two-sided alternative hypothesis is that there is a difference between two treatment groups.

The secondary null hypothesis is that there is no difference in the change from baseline of the average volume voided per micturition when treated with GSK1358820 compared to placebo. The secondary two-sided alternative hypothesis is that there is a difference between two treatment groups.

## 9.2. Sample Size Considerations

### 9.2.1. Sample Size Assumptions

The sample size for this study is hypothesized based on the observed treatment difference in the change from baseline of the daily average number of urinary incontinence episodes and the average volume voided per micturition at Week 12 from the integrated data of studies 191622-095/191622-520. It is assumed that the mean differences in the daily average number of urinary incontinence episodes and the average volume voided per micturition between GSK1358820 and placebo are -1.79 episodes/day and 30 mL from these studies results. Using the two sample t-test, 240 subjects in total (120 subjects for each treatment group) is required to achieve at least 89% power at the two-sided significance level of 5% to detect the assumed treatment differences for the daily average number of urinary incontinence episodes and the average volume voided per micturition simultaneously when common standard deviations (SD) are 3.5 episodes/day in the daily average number of urinary incontinence episodes and 70 mL in the average volume voided per micturition. This power is calculated by using power of each endpoint and Bonferroni inequality. Using above assumed values, power is 98% for the daily average number of urinary incontinence episodes and 91% for the average volume voided per micturition at the two-sided significance level of 5%. In this case, joint power is expected at least 89% (=98 + 91 -100) calculated by Bonferroni inequality.

The minimum detectable effect (i.e., the smallest observed effect size that could be statistically significant) based on the two sample t-test is a -0.9 episodes/day in the daily average number of urinary incontinence episodes and a 17.8mL in the average volume voided per micturition, respectively, when common standard deviations are 3.5 episodes/day in the daily average number of urinary incontinence episodes and 70 mL in the average volume voided per micturition.

### 9.2.2. Sample Size Sensitivity

In order to check sample size sensitivity, power of this study is calculated with a sample size of 120 subjects per treatment group in the following cases.

The mean difference of the daily average number of urinary incontinence episodes at week 12 between GSK1358820 and placebo of -1.69 to -1.89 episodes/day, and SD of 3 to 4 episodes/day under the condition that the mean difference and SD of the average volume voided per micturition is fixed as 30 mL and 70 mL (Table 4)

The mean difference of the average volume voided per micturition at week 12 between GSK1358820 and placebo of 25 to 35 mL, and SD of 60 to 80 mL under the condition that the mean difference and SD of the daily average number of urinary incontinence episodes is fixed as -1.79 episodes/day and 3.5 episodes/day (Table 5)

**Table 4 Power of this study under the condition of fixed mean difference and SD of the average volume voided per micturition**

Mean difference of the daily average number of urinary incontinence episodes between GSK1358820 and placebo	SD of the daily average number of urinary incontinence episodes between GSK1358820 and placebo		
	3.0	3.5	4.0
-1.69	90%	88%	82%
-1.79	91%	89%	85%
-1.89	91%	90%	87%

**Table 5 Power of this study under the condition of fixed mean difference and SD of the daily average number of urinary incontinence episodes**

Mean difference of the average volume voided per micturition between GSK1358820 and placebo	SD of the average volume voided per micturition between GSK1358820 and placebo		
	60	70	80
25	87%	77%	66%
30	95%	89%	81%
35	97%	95%	90%

### **9.2.3. Sample Size Re-estimation or Adjustment**

No sample size re-estimation is planned for this study.

## **9.3. Data Analysis Considerations**

### **9.3.1. Analysis Populations**

In this study, the subjects are permitted to receive re-treatment up to 2 times. When analyzing the 2nd treatment cycle, the population will consist of the subjects who had a 1st and 2nd treatment. When analyzing the 3rd treatment cycle, the population will consist of the subjects who had a 1st, 2nd and 3rd treatment.

### **Full Analysis Set (FAS)**

The FAS will be defined as all randomized subjects who have at least 1 post-baseline efficacy assessment. The FAS will be the primary population for all the efficacy analyses. The subjects will be analyzed according to the treatment group to which they were randomized.

### **Safety**

The Safety Population will be defined as all randomized subjects who received at least one dose of study drug. The Safety Population will be the population for all the safety analyses. The subjects will be analyzed according to the treatment group which they actually received.

### **Per-Protocol (PP)**

The PP Population will be defined as the subset of subjects in the FAS who do not have any major protocol violations. Details will be provided in the Reporting and Analysis Plan (RAP). The PP population will be only used to analyze until week 12 after first treatment, because the objective to use the PP population is to check the robustness of the primary and secondary efficacy endpoints.

### **9.3.2. Interim Analysis**

When all the subjects complete treatment phase 1 or week 24 of treatment phase 1 (except for the premature withdraw) data up to week 24 of treatment phase 1 may be locked, unblinded and analyzed for the regulatory submission.

## **9.4. Key Elements of Analysis Plan**

### **9.4.1. Primary Analyses**

The primary endpoint in this study is the change from baseline in the daily average number of urinary incontinence episodes at week 12 after the first treatment.

This will be analyzed using a mixed model for repeated measures (MMRM). This model will include the treatment group, site, visit, and treatment-by-visit interaction as fixed factors, baseline values and baseline-by-visit as covariates. An unstructured variance structure will be used to model the within-subject errors, shared across treatments. Analysis will be done with the MIXED procedure in SAS®, using the Kenward-Roger option to estimate denominator degrees of freedom and standard errors. Significant tests will be based on least-squares means using a two-sided 5% significance level (two-sided 95% confidence intervals). The dataset including only data until week 12 after the first treatment will be used for MMRM.

Sensitivity analysis under the assumption of missing not at random for missing data will be performed, because MMRM is valid only under the assumption of missing at random. This will be documented in RAP.

